14 PUBLICATION PLAN21
15 REFERENCES.....21

List of Abbreviations

ACEIs	Angiotensin converting enzyme inhibitors
AE	Adverse Event/Adverse Experience
ANP	Atrial natriuretic peptide
ARB	Angiotensin receptor blocker
BNP	Brain natriuretic peptide
CCaTS	Center for Clinical and Translational Science
CFR	Code of Federal Regulations
cGMP	Cyclic guanosine monophosphate
CHF	Congestive Heart Failure
CNP	c-type natriuretic peptide
CRF	Case Report Form
CRTU	Clinical Research and Trials Unit
DSMB	Data and Safety Monitoring Board
EF	Ejection Fraction
ES	Executive Secretary
FDA	Food and Drug Administration
GFR	Glomerular Filtration Rate
GCP	Good Clinical Practice
HF	Heart Failure
HFrEF	Heart Failure with Preserved Ejection Fraction
HFrEF	Heart Failure with Reduced Ejection Fraction
HIPAA	Health Insurance Portability and Accountability Act
HR	Hazard ratio
IB	Investigator's Brochure
IRB	Institutional Review Board
IV	Intravenous
LVEF	Left ventricular ejection fraction
NEP	Neprilysin
NEPi	Neprilysin inhibitor
NP	Natriuretic peptide
NPRC	Natriuretic peptide clearance receptor
NYHA	New York Heart Association

Study Summary

Title	A Proof of Concept Study to Determine the Efficacy of Entresto™ in heart failure with preserved ejection fraction (HFpEF) Based on Circulating Neprilysin Levels: The Circulating NEP and NEPi (CNEPi) Study
Running Title	CNEPi
Protocol Number	IRB # 18-000044
Phase	Phase 4
Methodology	Proof of Concept Study
Overall Study Duration	21 months
Subject Participation Duration	5 weeks
Single or Multi-Site	Mayo Clinic Sites
Objectives	Determine biomarker (plasma NT-proANP, NT-proBNP, NT-proCNP, cGMP) responses to Entresto™ in patients with HFpEF who have high and low serum NEP levels
Number of Subjects	40
Diagnosis and Main Inclusion Criteria	Subjects with NYHA 2-4 HFpEF
Study Product, Dose, Route, Regimen	Entresto™ 49/51 mg (sacubitril/valsartan) orally twice-daily
Duration of Administration	Up to 5 weeks
Reference therapy	NA
Statistical Methodology	Paired t-test comparing the change from baseline to up to 5 weeks after administration of Entresto™

1 Introduction

This document is a protocol for a human research study. This study will be carried out in accordance with the applicable United States government regulations and Mayo Clinic research policies and procedures.

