5.1 Description

Please see accompanying **Figure**. Study Intervention comprises of eligible HFpEF subjects who have provided informed consent and in whom blood will be collected (screening visit) to measure serum NEP levels and based on these levels will be assigned to a low or high NEP group. These subjects after having blood drawn at Visit 1 for baseline NEP, NT pro-ANP, -BNP,

-CNP and cGMP levels will then receive Entresto™ for up to 5 weeks. They will return in the 5th week for another blood draw to measure NEP, NT pro-ANP, -BNP, -CNP and cGMP levels. At visits 1 and 2 subjects will also provide urine samples for cGMP levels at baseline and post intervention analysis. Blood will also be collected and stored for future transcriptomic,

metabolomic and genomic studies.

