6.1 Screening Visit

Possible study participants will meet with study coordinator to review consent form. Medical history and current medications will be reviewed. Blood will be drawn for baseline serum NEP levels, safety laboratory tests (potassium, creatinine) and pregnancy test if necessary at the CRTU. Dependent on the results of the NEP levels which will be available within 48 hours, subjects will be assigned to a high or low NEP group. If subjects are found to be eligible and are on ACEi or ARBs, subjects will be instructed to withhold these drugs 36 hours before the initiation of treatment with Entresto™ at Visit 1 and throughout the duration of the study while subjects are on Entresto™.

6.2 Visit 1

Visit 1 will occur within 30 days of the Screening Visit. Qualified subjects will be evaluated as outpatients at the CRTU. Interim history, a review of medications, NYHA class assessment and a brief physical exam will be performed by a qualified study team member. Blood will be drawn for serum NEP levels, NT-proANP, NT-proBNP, NT-proCNP, cGMP and a pregnancy test will be performed, if necessary; urine sample will also be collected for cGMP levels. An additional 55 mL blood sample will be collected from subjects, for future transcriptomic, metabolomic and genomic analysis, who provide consent to allow their blood to be stored in the BAP laboratory for future studies. Subjects will be given the option to opt in or out of this component of the study. Following this, subjects will receive their first dose of Entresto™. BPs will be monitored at baseline prior to

administration of Entresto™ and 60 minutes after this first dose to ensure tolerance of the medication. Sitting systolic and diastolic BP will be monitored in the subject's dominant arm 3 times with an automatic blood-pressure monitor (Omron, Bannockburn, IL) and an average reading of these 3 measurements will be used. Before dismissal, subjects will be provided with Entresto™ tablets for the duration of the study. Study coordinator will follow-up with the subject by telephone on day 14 ± 5 post-visit 1 to monitor compliance and to assess tolerance.

6.3 Visit 2

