7.2 Statistical Methods

The primary analysis for this study will be a comparison of the changes in values of parameters of interest between the study groups low NEP vs. high NEP following up to 5 weeks of study drug intervention. This analysis will be completed using a paired t-test comparing the change from baseline to 5 weeks after study drug intervention. A secondary analysis will also be performed to evaluate the effects of the varying doses (in case, if the dose of the drug is changed during the course of the study). Analysis of variance methods will be used to compare changes from baseline to 6 hours, and pairwise group comparisons will be made via two-sample t-test if the overall ANOVA F-test is found to be significant. Distributions of changes will be examined and appropriate transformations applied prior to analyses, if necessary. Values will be expressed as the mean \pm SEM. A statistically significant difference will be considered to be present when $p < 0.05$.

8 Participant Safety and Adverse Events

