12.2 Core Laboratories

Mayo Clinic will serve as the core laboratory for measurement of serum NEP and other biomarkers. Plasma specimens will be collected at Study Visits (weeks 0, and 5), processed at the clinical centers according to the procedures provided by the core laboratory, and shipped to the core laboratory on dry ice (Refer to Biomarker Core Laboratory Manual of Procedures). Any subjects who agree to participate in the biorepository will have samples collected at the clinical sites stored at the Mayo Clinic BAP.

13 Study Finances

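### Section 7.2 ties its only between-group tests to a 6-hour change that is never sampled, and assigns the 5-week change a paired t-test that cannot compare low with high NEP

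*Combined protocol and SAP*

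**What the plan says.** Section 7.2 (Statistical Methods) makes three statements in sequence.

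1. The primary analysis compares the changes in the parameters of interest between the low and high NEP groups after up to 5 weeks of drug. The test is then named: "This analysis will be completed using a paired t-test comparing the change from baseline to 5 weeks after study drug intervention".
2. A secondary analysis will look at varying doses, should the dose be changed during the study.
3. "Analysis of variance methods will be used to compare changes from baseline to 6 hours". Groups are then to be compared two at a time by two-sample t-tests, but only when the F-test across all groups reaches significance.

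The Study Summary gives one method only: "Paired t-test comparing the change from baseline to up to 5 weeks after administration of Entresto™". It mentions neither 6 hours nor a between-group test. Section 7.1 plans 40 subjects, 20 in each NEP group.

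**The concern.** The third statement gives a time point that appears nowhere else in the document. If nothing is measured then, the analysis cannot be carried out.

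The consequence goes beyond one unusable sentence. The hypothesis in sections 1.2 and the primary analysis in 7.2 both set low against high NEP. The tests suited to that comparison are attached to the 6-hour change, while the test attached to the 5-week change does not compare groups. Taken literally, 7.2 leaves the primary question without a test that can be run. Someone would have to settle the test later, in an open-label study (section 5.7) and possibly with results in hand.

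**Working it through.** No formula governs this point. The check sets the analysis time point beside every place where samples or measurements are scheduled.

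**What is collected, and when**

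- *Screening (6.1, Schedule of Events):* NEP level and safety laboratory tests, before any drug.
- *Visit 1 (6.2):* blood for NEP, NT-proANP, NT-proBNP, NT-proCNP and cGMP, and urine for cGMP. Dosing comes afterwards: "Following this, subjects will receive their first dose of Entresto™". Blood pressure is read before "administration of Entresto™ and 60 minutes after this first dose to ensure tolerance of the medication". No blood or urine is scheduled after the dose that day.
- *Day 14 ± 5 (6.2, Schedule of Events):* a telephone call, with no sample.
- *Visit 2 (5.1, 6.3):* "They will return in the 5th week for another blood draw to measure NEP, NT pro-ANP, -BNP", NT-proCNP and cGMP. There is one blood draw and one urine sample.
- *Core laboratory (12.2):* "Plasma specimens will be collected at Study Visits (weeks 0, and 5"; no other time is given.
- *Early stoppers (4.6):* subjects with at least 2 weeks of drug have the Visit 2 assessments, with blood taken within 24 hours of stopping.

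**Distance from 6 hours**

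- Visit 2 as scheduled follows 4 completed weeks: 28 days × 24 = 672 hours or more after the first dose.
- The earliest Visit 2 that section 4.6 provides for follows 2 weeks of drug: 14 days × 24 = 336 hours.
- Biomarker samples scheduled at 6 hours: 0 per subject, so 0 of 40 subjects can contribute a 6-hour change.

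**Could 6 hours mean time since the last dose at Visit 2?** Section 6.3 asks only that the last dose be taken before the visit and sets no interval. It calls the Visit 2 blood pressure reading a baseline, but schedules no later reading or sample at that visit. The text does not support this interpretation.

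**Which named test can answer the primary question?**

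- *Paired t-test:* uses each subject's own before-and-after difference and asks whether the mean difference is zero. The 20 low-NEP and 20 high-NEP subjects are different people with no matching, so this test does not compare them.
- *Two-sample t-test:* compares the mean change in 20 subjects with the mean change in another 20. It fits the primary question, but 7.2 attaches it to the 6-hour change.
- *ANOVA F-test:* with two groups, F on 1 and 20 + 20 − 2 = 38 degrees of freedom equals the square of the pooled two-sample t on 38 degrees of freedom. As a gate before that t-test it adds nothing. With three or more groups, such as several dose levels, it is a separate test and the gate has a function.

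**The case against.** The strongest reply is that the ANOVA sentence may not belong to the primary analysis. It directly follows the secondary varying-dose analysis, and an overall F-test followed by pairwise comparisons is language for more than two groups. The primary time point is fixed elsewhere in 7.2 and in the Study Summary at up to 5 weeks. On that reading, the 6-hour phrase disables only one secondary sentence.

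Part of this stands. The text does not settle which analysis the sentence serves, so removing the F-test gate on a two-group assumption is not justified. The reply does not remove the problem. A dose analysis would have no 6-hour data either, and if the ANOVA and two-sample t-tests belong to it, the primary comparison is left with the paired t-test alone.

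Three stronger inferences are tempting and should not be drawn.

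- *That the trial sets out to measure an acute or single-dose response.* The objective (section 2), the endpoint (3.2) and the Study Summary make no such claim. The document does not explain where the 6-hour phrase came from.
- *That nobody is sampled between the pre-dose draw and week 5.* Section 4.6 allows an earlier Visit 2 draw for some subjects, though weeks rather than hours after the first dose.
- *That a 6-hour sample was left out of the schedule by mistake.* Sections 5.1, 6.2, 6.3 and 12.2 and the Schedule of Events agree on the sampling times, and the 6-hour phrase stands alone against them.

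**Conclusion.** Section 7.2 is wrong as written. Its planned analysis of the 6-hour change has no data for any of the 40 subjects. The tests placed there are the only ones named that can compare independent groups, and the 5-week change is otherwise given a test that cannot compare low with high NEP.

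The conclusion rests on the sampling schedule being complete as stated, and the sections that describe it are consistent. It does not depend on effect size, standard deviation or power, none of which is given in 7.1. It also holds whether the ANOVA sentence was meant for the primary or the secondary analysis; that affects only what should become of the F-test gate.

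The defect lies in the analysis text, not in the design. The samples needed for the primary comparison are already planned.

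**What to change.** Make three edits to 7.2 together; changing the time point alone would leave two competing tests on the same change, with neither marked as primary.

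1. Replace the 6-hour interval with *baseline (Visit 1, pre-dose) to Visit 2 (up to 5 weeks)*. The words in brackets cover the early Visit 2 draws allowed by section 4.6.
2. State that the primary low versus high NEP comparison of that change uses a two-sample test, and that the paired t-test is kept only for change within each group.
3. State whether the ANOVA with its F-test gate serves the secondary varying-dose analysis. If so, keep it there, applied to the same Visit 1 to Visit 2 change. If it was meant for the two NEP groups, the gate is redundant and can go.

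Bring the statistical line of the Study Summary into agreement, since it names only the paired t-test. Date the change, and record whether any Visit 2 biomarker results had been seen by then.

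The cost is a few sentences of text. No 6-hour draw, extra visit or additional subject is needed.

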1.1 Background

Heart failure with preserved ejection fraction (HFpEF) can result from abnormalities in the process of active relaxation and passive stiffness of the heart¹. The natriuretic peptides (NPs) play an important role in cyclic guanosine monophosphate (cGMP) mediated inhibition of cardiomyocyte growth, smooth muscle and fibroblast proliferation and collagen deposition that can affect passive stiffness²⁻⁴. Further, NPs can attenuate angiotensin-II, endothelin-1 and arginine-vasopressin induced increased proliferation of vascular smooth muscle cells⁵. HFpEF is characterized by elevated intra-cardiac pressures⁶ and the natriuretic and diuretic properties of NPs play a pivotal role in maintaining normal volume homeostasis^{7, 8}. Natriuretic peptides also reduce peripheral vascular resistance and blood pressure⁹. The NPs additionally inhibit the effects of the renin-angiotensin-aldosterone and sympathetic nervous system¹⁰⁻¹³ the maladaptive activation of which results in the clinical syndrome of HF. Nephilysin (NEP) mediates the anti-fibrotic, anti-proliferative, myocardial relaxation, vasodilator and diuretic properties of NPs by maintaining NP homeostasis. NPs are degraded and cleared by NEP and the NP clearance receptor (NPRC) respectively. NEP inhibition (NEPi) therefore results in significant increases in plasma BNP, urinary BNP and urinary sodium, increases in cardiac output and reduction in intra-cardiac filling pressures¹⁴.

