1.2 Preliminary Data

Entresto™, a crystalline complex of a NEPi (sacubitril) and an angiotensin receptor blocker (ARB, valsartan), was recently approved to treat NYHA Class 2-4 patients with HFpEF after the PARADIGM-HF trial was stopped early due to an overwhelming benefit of the drug in reducing all-cause mortality (hazard ratio [HR]: 0.84; p<0.001), CV mortality (HR 0.80; p<0.001), hospitalization for HF (HR 0.79; p<0.001) and in addition reduced the symptoms and physical limitations of HF by 21% (p=0.001)¹⁵. Entresto™ due to its additional NEPi activity could be a promising new therapy for HFpEF. Entresto™ when administered to patients with HFpEF in a phase 2 study resulted in significantly reduced NT-proBNP levels, a surrogate marker of LV wall stress and NEP activity, as compared to being treated with valsartan alone¹⁶. Entresto™ therefore is being tested as treatment for HFpEF in a Phase 3 trial, PARAGON-HF, evaluating its efficacy in reducing CV death and HF hospitalizations as compared to valsartan.

NEP is a cell membrane bound metalloendopeptidase and can be released from the cell surface, resulting in the formation of a circulating peptide that maintains its catalytic activity^{17, 18}. In recent clinical studies, circulating NEP levels were significantly associated with the composite endpoint of cardiovascular death or HF hospitalization (HR 1.17; p=0.001) and cardiovascular death (HR: 1.19; p=0.002) in patients with HF¹⁹. The PARAGON-HF trial includes all-comers with HFpEF; the final data collection will be completed May 2019. It is being increasingly recognized that HFpEF is a disease entity that has considerable phenotypic heterogeneity^{20, 21}. Therefore, targeting all-comers who suffer from a heterogeneous disease process using a single treatment intervention may not result in desirable outcomes as has been evident with multiple prior negative HFpEF trials^{22, 23}. The importance of biomarker based clinical trials that deliver the right drug to the right patient is being increasingly recognized as a useful strategy to limit sample size and decrease costs by enriching such trials with potential responders^{24, 25}. Whether the beneficial effects of Entresto™ therapy are dependent on baseline NEP levels is unknown and is being explored in this study. The **hypothesis** in this proof of concept study is that

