3.2 Primary Study Endpoints

The primary endpoint measured is change in biomarkers with Entresto™ administration that reflect NEP activity and myocardial stress (NT pro-ANP, -BNP, -CNP) and drug action (cGMP). This endpoint has been well validated as a measure of Entresto™ drug response.

4 Subject Selection Enrollment and Withdrawal

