4.1 Inclusion Criteria

1. Age ≥ 50 years
2. LVEF $\geq 45\%$ assessed by echocardiography, nuclear scan, MRI or left ventriculogram within the past 24 months

3. Current New York Heart Association (NYHA) class 2-4 symptoms of heart failure (HF)
4. Stable medical therapy for 30 days as defined by:
 - a. No addition or removal of ACE, ARB, beta-blockers, calcium channel blockers (CCBs) or aldosterone antagonists
 - b. No change in dosage of ACE, ARBs, beta-blockers, CCBs or aldosterone antagonists of more than 100%
5. Elevated NT-proBNP (>300 pg/ml) or BNP (>200 pg/ml)
6. One of the following within the last 24 months
 - a. Previous hospitalization for HF with radiographic evidence of pulmonary congestion (pulmonary venous hypertension, vascular congestion, interstitial edema, pleural effusion) **or**
 - b. Catheterization documented elevated filling pressures at rest (LVEDP \geq 15 or PCWP \geq 20) or with exercise (PCWP \geq 25) **or**
 - c. Echo evidence of diastolic dysfunction / elevated filling pressures (**at least two**)
 - i. E/A > 1.5 + decrease in E/A of > 0.5 with valsalva
 - ii. Deceleration time \leq 140 ms
 - iii. Pulmonary vein velocity in systole < diastole (PVs<PVd) (sinus rhythm)
 - iv. E/e' \geq 15
 - v. Left atrial enlargement (\geq moderate)
 - vi. Pulmonary artery systolic pressure > 40 mmHg
 - vii. Evidence of left ventricular hypertrophy
 1. LV mass/BSA \geq 96 (♀) or \geq 116 (♂) g/m²
 2. Relative wall thickness \geq 0.43 (♂ or ♀) [(IVS+PW)/LVEDD]
 3. Posterior wall thickness \geq 0.9 (♀) or 1.0 (♂) cm

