7.1 Sample Size Determination

The sample size calculation and statistical analysis have been designed in collaboration with the Division of Biostatistics. This is a proof of concept study; 40 subjects will be recruited, with 20 in each group (Group 1: subjects with HFpEF - low NEP levels and, Group 2: subjects with HFpEF - high NEP levels). It is anticipated that 100 subjects will be screened.

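### Does leaving the scale of biomarker change open in section 7.2 undermine the low-versus-high NEP comparison?

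*Combined protocol and SAP*

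**What the plan says.** Section 3.2 defines the endpoint without a scale: "The primary endpoint measured is change in biomarkers", covering three N-terminal natriuretic peptide fragments and cGMP. Section 7.2 describes the primary analysis as "a comparison of the changes in values of parameters of interest between the study groups low NEP vs. high NEP". On scale it says only "Distributions of changes will be examined and appropriate transformations applied prior to analyses, if necessary". It names no transformation and no criterion for needing one. It does not say whether a transformation would apply to the changes or to the Visit 1 and Visit 2 values before they are subtracted. Summaries are equally general: "Values will be expressed as the mean", with SEM. The Study Summary and section 2 add nothing on scale.

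Sections 3.1 and 5.3 make this a single-arm study with groups formed by a measured NEP cut-off of 1.55 ng/ml. Section 7.1 sets its size and ambition: "This is a proof of concept study; 40 subjects will be recruited, with 20 in each group".

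**The concern.** Randomisation does not balance baseline biomarker levels here, and two statements in the background make an imbalance conceivable. Section 1.1 says "NPs are degraded and cleared by NEP and the NP clearance receptor (NPRC) respectively". Section 1.2 speaks of "NT-proBNP levels, a surrogate marker of LV wall stress and NEP activity". If the drug lowers a marker by the same proportion in everyone, the group that starts higher has the larger absolute fall.

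The hypothesis in sections 1.2-1.3 is that response differs by NEP level. A difference produced only by the scale would look like support for it, and one hidden by the scale would look like evidence against it. Settling the scale after the changes have been seen, in an open-label study, also leaves room to choose the more favourable result.

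**Working it through.** **Inputs.** From the documents: 20 + 20 = 40 subjects and p<0.05 (two-sided assumed). They give no effect size, SD, power or baseline level by NEP group, so the plan has no figure to reproduce. Everything else is assumed: log-normal marker, geometric mean 600 in the reference group, SD of log baseline 0.6, SD of log change 0.25. The mild case uses SDs of 0.7 and 0.35.

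**Step 1: how scale and baseline interact.**
- Same 30% fall from 600 and from 1200: 0.7 × 600 − 600 = −180 and 0.7 × 1200 − 1200 = −360. The absolute changes differ two-fold; the log ratio is ln 0.7 = −0.357 in both.
- Same fall of 60 units: ln(540/600) = −0.105 and ln(1140/1200) = −0.051. Now the log ratios differ about two-fold and the absolute changes agree.

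Neither scale is safe without knowing how the drug acts on that marker.

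**Step 2: false positives when both groups have the same 30% fall.** Simulated trials with 20 per group, using a two-sample t-test (Welch for raw change, pooled for log ratio). The rule in section 7.2 is represented by a Shapiro test on within-group changes, followed by a transformation if it rejects, which happens in 75-79% of trials.

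| Baseline ratio | 1 | 1.25 | 1.5 | 2 |
|---|---|---|---|---|
| Raw change, never transformed | 4% | 10% | 21% | 50% |
| Log ratio always | 5% | 5% | 5% | 5% |
| Rule, then log the values | 5% | 7% | 11% | 17% |
| Rule, then cube root of the changes | 6% | 9% | 17% | 34% |

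The log-ratio row holds at 5% by construction, because the data were generated as proportional.

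With mild inputs (15% fall), raw change gives 6% and 8% at ratios 1.5 and 2, and the rule gives 6-7% with either transformation. Raw change then needs a 2.44-fold baseline gap to reach 10%.

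**Step 3: false positives when both groups have the same absolute change** (noise SD 60), at baseline ratios 1.5 and 2.
- Log ratio always, ±60 units: 12-13% and 27-30%.
- Log ratio always, ±120 units: 21-29% and 53-68%.
- Raw change: 5%.
- Rule, then log the values: 6-8%, because the changes are then close to normal and are seldom transformed.

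**Step 4: power at equal baselines.**
- 0% against 25% fall: raw 82%, log ratio 94%, rule with logged values 91%.
- 0 against −60 units: raw 87%, log ratio 64%.

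**Step 5: would a fixed log ratio settle the baseline question?** Not by itself, since it is still a change score. Suppose log values show no group effect given baseline, with correlation 0.5-0.7 and a baseline gap of 0.5-0.8 SD. The change-score test then rejects in 9-23% of trials and a baseline-adjusted model in about 5%. If instead the baseline is measured with classical error, the adjusted model rejects in 21% and 42% at ratios 1.5 and 2 (correlation 0.5), or 10% and 18% (correlation 0.8). Which model is preferable depends on facts the documents do not contain.

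**The case for a change.** The strongest case for a change is that the wording permits poor choices as well as good ones. Transforming the changes is a literal reading of the sentence, and in the proportional scenario it leaves 17% and 34% false positives. Even the sensible reading gives 17% at a two-fold gap. Raw change can also hide a real difference: with falls of 15% and 30% and the high-NEP baseline one third lower, power is 13% on raw change against 67% on the log ratio. Trying both scales and keeping the significant one gives 8% at equal baselines. Fixing the scale would cost only a few sentences and a rule for values below the assay limit.

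Much of this is arithmetically right, and it is true that no section fixes the scale. Its weight is limited for three reasons:
- The plan places the transformation before the analysis, after a look at distributions. Testing on two scales and keeping the better p-value is not what it describes.
- Changes can be negative, so a log cannot be taken of them directly. An analyst who decides that skewed biomarkers need a log has to apply it to the Visit 1 and Visit 2 values, which is the reading that works for proportional effects.
- The larger rates need a sizeable baseline gap and a proportional effect together. Section 1.1 concerns degradation of the peptides, whereas the endpoint measures NT-pro fragments and cGMP. Calling NT-proBNP a marker of NEP activity, as section 1.2 does, gives no level by NEP group.

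The naming of a paired t-test for a between-group comparison is a separate matter, not judged here.

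**Conclusion.** No change to the plan is needed. The scale is an unwritten detail, and section 7.2 already has a procedure for settling it: look at the distributions, then transform before analysis. Under a proportional effect and the main assumed inputs, that procedure with logged values keeps false positives at about 5%, 7%, 11% and 17% for baseline ratios of 1, 1.25, 1.5 and 2. It keeps most of the power of the log ratio (91% against 94%), and under an additive effect it holds at 6-8%.

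A log ratio required for all four markers would do better in the first situation and much worse in the second (12-68%). The documents do not show which situation applies to which marker, and whether to adjust for baseline is also unsettled. That makes it a trade-off, not a correction.

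The conclusion assumes that analysts log the values rather than transform the changes, and that they do not choose the scale by its p-value. All rates rest on assumed SDs, effects and baseline ratios, so they show direction and range only. In a proof of concept with 20 per group, noting the scale for each marker before Visit 2 results are opened, and tabulating baseline levels by group, would be good housekeeping that requires no amendment.
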